5.2.4.2 Continuous ECG monitoring

Not applicable.

5.2.5 Other safety parameters

5.2.5.1 Local tolerability

Local tolerability will be assessed by the investigator on the basis of ‘swelling’, ‘induration’, ‘heat’, ‘redness’, ‘pain’, or ‘other findings’.

5.2.5.2 Suicidality assessment

Not applicable.

5.2.6 Assessment of adverse events

5.2.6.1 Definitions of adverse events

5.2.6.1.1 Adverse event

An adverse event (AE) is defined as any untoward medical occurrence in a patient or clinical investigation patient administered a medicinal product and which does not necessarily have to have a causal relationship with this treatment.

An AE can therefore be any unfavourable and unintended sign (including an abnormal laboratory finding), symptom, or disease temporally associated with the use of a medicinal product, whether or not considered related to the medicinal product.

The following should also be recorded as an AE in the CRF and BI SAE form (if applicable):

- Worsening of the underlying disease or of other pre-existing conditions
- Changes in vital signs, 12-lead ECG, physical examination, and laboratory test results, if they are judged clinically relevant by the investigator

If such abnormalities already pre-exist prior to trial inclusion, they will be considered as baseline conditions and should be collected in the eCRF only.

5.2.6.1.2 Serious adverse event

A SAE is defined as any AE which fulfils at least one of the following criteria:

- Results in death
- Is life-threatening, which refers to an event in which the patient was at risk of death at the time of the event; it does not refer to an event that hypothetically might have caused death if more severe,
- Requires inpatient hospitalisation
- Requires prolongation of existing hospitalisation
- Results in persistent or significant disability or incapacity
- Is a congenital anomaly/birth defect
- Is deemed serious for any other reason if it is an important medical event when based upon appropriate medical judgment which may jeopardise the patient and may require medical or surgical intervention to prevent one of the other outcomes listed in the above

Proprietary confidential information © 2021 Boehringer Ingelheim International GmbH or one or more of its affiliated companies

definitions. Examples of such events are intensive treatment in an emergency room or at home for allergic bronchospasm, blood dyscrasias or convulsions that do not result in hospitalisation or development of dependency or abuse

5.2.6.1.3 AEs considered ‘Always Serious’

Cancers of new histology and exacerbations of existing cancer must be classified as a serious event regardless of the time since discontinuation of the trial medication and must be reported as described in [section 5.2.6.2.1](#), subsections ‘AE Collection’ and ‘AE reporting to sponsor and timelines’.

In accordance with the European Medicines Agency initiative on Important Medical Events, BI has set up a list of further AEs, which by their nature, can always be considered to be ‘serious’ even though they may not have met the criteria of an SAE as given above.

The latest list of ‘Always Serious AEs’ can be found in the EDC system, a remote data capture system which allows the entry of trial data at the trial site. These events should always be reported as SAEs as described above.

5.2.6.1.4 Adverse events of special interest

The term AEs of special interest (AESI) relates to any specific AE that has been identified at the project level as being of particular concern for prospective safety monitoring and safety assessment within this trial, e.g. the potential for AEs based on knowledge from other compounds in the same class. AESIs need to be reported to the sponsor’s Pharmacovigilance Department within the same timeframe that applies to SAEs, please see [section 5.2.6.2.2](#).

The following are considered as AESIs in this trial:

- Hepatic injury, as defined by the following alterations of hepatic laboratory parameters:
 - an elevation of AST and/or ALT \geq 3-fold ULN combined with an elevation of total bilirubin \geq 2-fold ULN measured in the same blood sample, or
 - ALT, and/or AST elevations \geq 10-fold ULN

These lab findings constitute a hepatic injury alert and the subjects showing these lab abnormalities need to be followed up according to the ‘DILI checklist’ provided in the ISF. In case of clinical symptoms of hepatic injury (icterus, unexplained encephalopathy, unexplained coagulopathy, right upper quadrant abdominal pain, etc.) without lab results (ALT, AST, total bilirubin) available, the Investigator should make sure these parameters are analysed, if necessary in an unscheduled blood test. Should the results meet the criteria of hepatic injury alert, the procedures described in the DILI checklist should be followed.

- Systemic hypersensitivity including infusion reaction and anaphylactic reaction:
 - Any suspicion of severe infusion reaction systemic/hypersensitivity reaction and of any potential cases of anaphylaxis should be defined and assessed using the criteria discussed in the statement paper from Sampson HA ([Appendix 10.1.3, R11-4890](#)).
- Severe infections (according to RCTC grading in ISF)

Proprietary confidential information © 2021 Boehringer Ingelheim International GmbH or one or more of its affiliated companies

- Opportunistic and mycobacterium tuberculosis infections
 - These include pneumocystis jirovecii, BK virus disease including PVAN, CMV, post-transplant lymphoproliferative disorder (EBV), progressive multifocal leucoencephalopathy, bartonellosis (disseminated only), blastomycosis, toxoplasmosis, coccidioidomycosis, histoplasmosis, aspergillosis (invasive only), candidiasis (invasive or pharyngeal), cryptococcosis, other invasive fungi (mucormycosis (zygomycosis, rhizopus, mucor, lichtheimia), scedosporium/pseudallescheria boydii, fusarium), legionellosis, listeria monocytogenes (invasive only), tuberculosis, nocardiosis, non-tuberculous mycobacterium, salmonellosis (invasive only), hepatitis B virus [HBV] reactivation, herpes simplex (invasive only), herpes zoster, strongyloides (hyperinfection syndrome and disseminated forms only), paracoccidioides, penicillium marneffei, sporothrix schenckii, cryptosporidium species (chronic only), microsporidiosis, leishmaniasis (visceral only), trypanosoma cruzi infection (Chagas' disease) (disseminated only), campylobacteriosis (invasive only), shigellosis (invasive only), vibriosis (invasive due to vibrio vulnificus), hepatitis C virus [HCV] progression ([R17-2617](#)).

5.2.6.1.5 Intensity (severity) of AEs

The intensity (severity) of the AE should be judged based on the following:

- Mild: Awareness of sign(s) or symptom(s) that is/are easily tolerated
- Moderate: Sufficient discomfort to cause interference with usual activity
- Severe: Incapacitating or causing inability to work or to perform usual activities

5.2.6.1.6 Causal relationship of AEs

Medical judgment should be used to determine the relationship, considering all relevant factors, including pattern of reaction, temporal relationship, de-challenge or re-challenge, confounding factors such as concomitant medication, concomitant diseases and relevant history.

Arguments that may suggest that there is a reasonable possibility of a causal relationship could be:

- The event is consistent with the known pharmacology of the drug
- The event is known to be caused by or attributed to the drug class
- A plausible time to onset of the event relative to the time of drug exposure
- Evidence that the event is reproducible when the drug is re-introduced
- No medically sound alternative aetiologies that could explain the event (e.g. pre-existing or concomitant diseases, or co-medications)
- The event is typically drug-related and infrequent in the general population not exposed to drugs (e.g. Stevens-Johnson syndrome)
- An indication of dose-response (i.e. greater effect size if the dose is increased, smaller effect size if dose is reduced)

Proprietary confidential information © 2021 Boehringer Ingelheim International GmbH or one or more of its affiliated companies

Arguments that may suggest that there is no reasonable possibility of a causal relationship could be:

- No plausible time to onset of the event relative to the time of drug exposure is evident (e.g. pre-treatment cases, diagnosis of cancer or chronic disease within days/weeks of drug administration; an allergic reaction weeks after discontinuation of the drug concerned).
- Continuation of the event despite the withdrawal of the medication, taking into account the pharmacological properties of the compound (e.g. after 5 $t_{1/2}$). Of note, this criterion may not be applicable to events whose time course is prolonged despite removing the original trigger.
- Additional arguments amongst those stated before, like alternative explanation (e.g. situations where other drugs or underlying diseases appear to provide a more likely explanation for the observed event than the drug concerned).
- Disappearance of the event even though the trial medication treatment continues or remains unchanged.

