1.2.6 Residual Effect Period

The residual effect period (REP) of Spesolimab is 16 weeks. This is the period after the last dose with measurable drug levels and/or PD effects still likely to be present.

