2.1.3 Secondary endpoint

The occurrence of treatment-emergent AEs.

[figure not shown]
The occurrence of drug-related AEs.

[figure not shown]

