3.3.4.3 Discontinuation of the trial by the sponsor

Boehringer Ingelheim (BI) reserves the right to discontinue the trial at any time for any of the following reasons:

1. Failure to meet expected enrolment goals overall or at a particular trial site.
2. New toxicological findings, SAEs, or any safety information invalidating the earlier positive benefit-risk assessment. Dose escalation will be terminated if more than 50% of the subjects at one dose level show drug-related and clinically-relevant AEs of moderate or severe intensity, or if at least one drug-related SAEs is reported.
3. Violation of GCP or the clinical trial protocol (CTP) or the contract with BI impairing the appropriate conduct of the trial.
4. The sponsor decides to discontinue the further development of the investigational product.
5. Dose escalation will be stopped if at least two subjects at one dose level have relevant individual QT prolongations, i.e. a QTc increase of greater than 60 ms from baseline in connection with absolute QT or QTc greater than 500 ms, as confirmed by a repeated ECG recording. The investigator/trial site will be reimbursed for reasonable expenses incurred in case of trial termination (except if item three applies).

Proprietary confidential information © 2021 Boehringer Ingelheim International GmbH or one or more of its affiliated companies

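### The causality guidance gives a late allergic reaction as an example of implausible timing, which conflicts with the protocol's own 16-week residual effect period after a single dose and may lower the drug-related AE count

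*Protocol*

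**What the plan says.** Protocol section 5.2.6.1.6 opens by leaving the decision to the assessor: "Medical judgment should be used to determine the relationship, considering all relevant factors, including pattern of reaction, temporal relationship". It then gives two lists. The list in favour of a link includes "A plausible time to onset of the event relative to the time of drug exposure". The list against is introduced by "Arguments that may suggest that there is no reasonable possibility of a causal relationship could be". Its first item concerns implausible timing relative to exposure, and one of the bracketed examples is "an allergic reaction weeks after discontinuation of the drug concerned". The second item concerns events that persist after withdrawal. Only that item carries the qualifier "taking into account the pharmacological properties of the compound", with five half-lives as its example.

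Protocol section 1.2.6 sets the REP at 16 weeks and defines it thus: "This is the period after the last dose with measurable drug levels and/or PD effects still likely to be present". SAP section 6.1 runs the on-treatment phase from administration (or start of infusion) to 16 weeks after administration (or end of infusion).

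The causality label is used in two places that matter here. One is a secondary endpoint in protocol section 2.1.3, "The occurrence of drug-related AEs", which has its own table under SAP section 7.8.1. The other is protocol section 3.3.4.3, where escalation ends "if at least one drug-related SAEs is reported", or when more than half of the subjects at a dose level have drug-related, clinically relevant AEs of moderate or severe intensity.

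**The concern.** The example suits a drug that is cleared quickly. Here a subject who reacts four weeks after the only dose is on treatment according to the SAP, is inside the REP according to the protocol, and yet matches the protocol's illustration of implausible timing. An assessor who follows the illustration would lean towards calling the event unrelated.

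The trial is open-label and has no placebo group, so no control rate exists against which a shift in causality calls could be seen. The event type concerned, systemic hypersensitivity, is one the protocol lists as an AESI. Post-baseline ADA sampling begins on Day 15, within the period the example discounts. At stake is a possible downward shift in one of the two secondary endpoints, and in a label that escalation decisions use.

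**Working it through.** **Inputs**
- REP: 16 weeks (protocol 1.2.6), carried into the SAP's on-treatment phase (SAP 6.1).
- Half-life: about three weeks in ADA-negative and about one week in ADA-positive GPP patients (protocol 1.2.4); four weeks (protocol 3.2). The protocol does not reconcile the three- and four-week figures.
- One dose per subject (protocol 4.1.4); 10 subjects per dose group, three IV and two SC groups (protocol 3.1).
- At least two weeks between the first dosings of successive cohorts within a route (protocol 3.1).

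**Step 1: the plan's own figure.** The protocol gives no formula for the 16-week REP, so it can only be checked for plausibility. Five half-lives are 5 × 3 = 15 weeks, 5 × 4 = 20 weeks and 5 × 1 = 5 weeks. Sixteen weeks is consistent with the three- to four-week range.

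**Step 2: how much drug is present weeks after the dose.** Assume mono-exponential decline, so the fraction remaining is 0.5^(t / half-life).

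| Half-life | 5 half-lives | Week 2 | Week 3 | Week 4 | Week 8 | Week 16 |
|---|---|---|---|---|---|---|
| 1 week (ADA-positive) | 5 weeks | 25% | 12.5% | 6.3% | 0.4% | <0.01% |
| 3 weeks | 15 weeks | 63% | 50% | 40% | 16% | 2.5% |
| 4 weeks | 20 weeks | 71% | 59% | 50% | 25% | 6.3% |

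At three to four weeks' half-life, a reaction some weeks after the dose falls in a period of substantial exposure. At one week it is still within five half-lives up to week 5. These figures describe exposure only. They do not measure misclassification.

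**Step 3: does the surrounding text repair the example?** The pharmacology qualifier belongs to the item on persisting events. The timing item does refer to exposure, but its bracketed example tells the reader how timing is to be judged for allergic reactions, and nothing adapts it to a long half-life or to a single dose.

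**Step 4: effect on the endpoint per reclassified subject.** For a subject whose only drug-related AE is judged unrelated, the incidence falls by 1/10 = 10 percentage points in a dose group, 1/30 = 3.3 points over the IV groups and 1/20 = 5 points over the SC groups.

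**Step 5: effect on escalation.** At the minimum spacing, the first 450 mg subject is 2 + 2 = 4 weeks past dosing when the 1200 mg cohort starts, so an event weeks after dosing can precede an escalation step. For the SAE criterion a single label decides. The other criterion needs at least 6 of 10 subjects, so one label matters only at that boundary.

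**Step 6: what does not depend on the label.** Treatment-emergent AEs are counted for 16 weeks whatever the causality (protocol 2.1.3, SAP 6.1). Systemic hypersensitivity is an AESI without a causality condition (protocol 5.2.6.1.4) and is reported within 24 hours (protocol 5.2.6.2.2). The SAP's hypersensitivity, anaphylaxis and angioedema searches (SAP 7.8.1) have no causality filter. After the end-of-trial visit only related AESIs are reported (protocol 5.2.6.2.1), but that visit is scheduled for Day 176, beyond the 112 days of the REP.

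**The case against.** The strongest reply is that this is one bracketed illustration in a generic list of arguments that only may suggest something, under an instruction to weigh every relevant factor. Other items in the section, such as re-introduction of the drug, dose reduction or continued treatment, cannot apply to a single dose either, so assessors must already choose what fits. Measured against exposure, a reaction at week 6 has a plausible onset, which the same section counts in favour of a link. This stands as a limit on the effect: the text does not direct anyone to a conclusion. It does not remove the conflict, because an item that merely cannot apply is harmless, whereas this one can be applied and points the wrong way.

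A reader might infer that delayed reactions are systematically removed from the endpoint and that the drug-related rate is biased low. The documents do not support that: the wording is permissive, and nothing in them gives a misclassification rate. A reader might also take the share of the 16-week window lying beyond two weeks, (112 − 14)/112 = 87.5%, as the size of the problem. That is a count of calendar days after a chosen cut-off, since the protocol says only weeks. Nor does the protocol say that the drug stays active for 16 weeks: it says that levels and/or effects are still likely, and ADA-positive patients clear it faster.

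On escalation, the protocol has further routes that need no causality label: the sponsor may act on any safety information that overturns the benefit-risk assessment (3.3.4.3), the investigator may interrupt escalation (3.1), and the next dose requires the absence of safety concerns (1.4). Many late events could also arise after the next cohort has started. Both points reduce the weight of the escalation argument without cancelling it.

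**Conclusion.** The conflict between protocol sections 5.2.6.1.6 and 1.2.6 is real and is not resolved elsewhere in the protocol or the SAP. Its likely effect is small and its severity minor. The example may lead an assessor to class a delayed hypersensitivity reaction as unrelated; if so, the drug-related AE incidence falls by 10 percentage points per affected subject in a group of 10, and a drug-related escalation criterion might not be met when it otherwise would. The events themselves would still appear among treatment-emergent AEs and in the AESI and hypersensitivity displays; only the related label would be lost.

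This rests on three assumptions: that discontinuation means the single dose; that the half-lives quoted from patients and from the design section are a fair guide for these healthy subjects; and, for the residual fractions, that decline is mono-exponential. The direction of any error is towards unrelated, but its frequency cannot be derived from the documents. The trial is exploratory and tests no hypothesis, so no inferential result is affected.

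**What to change.** Reconcile section 5.2.6.1.6 with section 1.2.6. Remove the allergic-reaction example or adapt it, and add one sentence: in this single-dose trial, plausibility of onset is judged by time since dosing, in light of the REP and the compound's pharmacology, and not by time since discontinuation. Referring to the REP as context is better than making its end a new cut-off, because the REP is defined by drug levels and effects and not by hypersensitivity risk. Repeat the sentence in the site's AE training. The escalation criteria need no change for this purpose.

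The cost is one sentence in the protocol and one in the training material. The downside is that a few more late events may be classed as drug-related, so the reported rate may look slightly less favourable.

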5.2.6.2 Adverse event collection and reporting

5.2.6.2.1 AE collection

Upon enrolment into a trial, the subjects baseline condition is assessed (for instance, by documentation of medical history/concomitant diagnoses), and relevant changes from baseline are noted subsequently.

Subjects will be required to report spontaneously any AEs as well as the time of onset, end time, and intensity of these events. In addition, each subject will be regularly assessed by the medical staff throughout the clinical trial and whenever the investigator deems necessary. As a minimum, subjects will be questioned for AEs (and concomitant therapies) at the time points indicated in the [Flow Chart](#). Assessment will be made using non-specific questions such as 'How do you feel?' Specific questions will be asked wherever necessary in order to more precisely describe an AE.

A careful written record of all AEs shall be kept by the investigator in charge of the trial. Records of AEs shall include data on the time of onset, end time, and intensity of the event as well as any treatment or action required for the event and its outcome.

The following must be collected and documented on the appropriate CRF(s) by the investigator:

- From signing the informed consent onwards until an individual subject's EoTrial:
 - All AEs (serious and non-serious) and all AESIs.
 - The only exception to this rule are AEs (serious and non-serious) and AESIs in Phase I trials in healthy subjects, when subjects discontinue from the trial due to screening failures prior to administration of any trial medication. In these cases, the subjects' data must be collected at trial site but will not be entered in the CRF or trial database and will not be reported in the CTR.

Proprietary confidential information © 2021 Boehringer Ingelheim International GmbH or one or more of its affiliated companies

- After the individual subject's EoTrial:
 - The investigator does not need to actively monitor the subject for new AEs but should only report any occurrence of cancer and related SAEs and related AESIs of which the investigator may become aware of by any means of communication, e.g. phone call. Those AEs should, however, not be reported in the CRF.

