3.3.4 Withdrawal of subjects from treatment or assessments

Subjects may discontinue trial treatment or withdraw consent to trial participation as a whole ('withdrawal of consent') with very different implications; please see sections 3.3.4.1 and [3.3.4.2](#).

If a subject is removed from or withdraws from the trial prior to the first administration of trial medication, the data of this subject will not be entered in the case report form (CRF) and will not be reported in the clinical trial report (CTR). If a subject is removed from or withdraws from the trial after the first administration of trial medication, this will be documented and the reason for discontinuation must be recorded in the CRF; in addition, the data will be included in the CRF and will be reported in the CTR.

At the time of discontinuation, a complete EoTrial examination will be performed, if possible, and the information will be recorded in the CRF. If the discontinuation occurs before the end of the REP (see [section 1.2.6](#)), the discontinued subject should if possible be questioned for AEs and concomitant therapies at or after the end of the REP in order to ensure collection of AEs and concomitant therapies throughout the REP, if not contrary to any consent withdrawal of the subject.

If it is known that a subject becomes pregnant during the trial, administration of the trial medication is to be stopped immediately, and the subject is to be removed from the trial. The subject is to be followed until she has given birth or until the end of the pregnancy. The subject's data are to be collected until the end of the trial (last visit of last subject) and reported in the CTR. For the reporting of pregnancy and associated events, refer to [section 5.2.6.2.4](#).

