3.3.4.1 Discontinuation of trial treatment

An individual subject will discontinue trial treatment if:

1. The subject wants to discontinue trial treatment, without the need to justify the decision
2. The subject has repeatedly shown to be non-compliant with important trial procedures and, in the opinion of both the investigator and sponsor representative, is not willing or able to adhere to the trial requirements in the future
3. The subject needs to take concomitant medication that interferes with the investigational medicinal product or other trial treatment

Proprietary confidential information © 2021 Boehringer Ingelheim International GmbH or one or more of its affiliated companies

4. The subject can no longer receive trial treatment for medical reasons (such as pregnancy, surgery, AEs, or diseases)
5. An AE or clinically significant laboratory change or abnormality occurs that the investigator assesses as warranting discontinuation of treatment. This may include cases of sustained symptomatic hypotension (BP <90/50 mmHg) or hypertension (BP >180/100 mmHg), clinically relevant changes in 12-lead ECG requiring intervention, or unexplained hepatic enzyme elevations at any time during the trial
6. The subject has an elevation of AST and/or ALT \geq 3-fold ULN and an elevation of total bilirubin \geq 2-fold ULN (measured in the same blood sample) and/or needs to be followed up according to the DILI checklist provided in the ISF

In addition to these criteria, the investigator may discontinue subjects at any time based on his or her clinical judgment.

Even if the trial treatment is discontinued, the subject remains in the trial and, given his/her agreement, will undergo the procedures for early treatment discontinuation and follow up as outlined in the [Flow Chart](#) and [section 6.2.3](#).

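### For a dosed subject who leaves before the 16-week residual effect period ends, protocol 3.3.4 asks for adverse events across that whole period, but 5.2.6.2.1 can keep some of them, most clearly related SAEs and AESIs, out of the trial database

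*Protocol*

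**What the plan says.** **Protocol 3.3.4 (withdrawal of subjects).** For a subject who leaves after dosing: "At the time of discontinuation, a complete EoTrial examination will be performed, if possible". If this falls before the end of the REP, the subject should, if possible and unless the withdrawal of consent rules it out, be asked about AEs and concomitant therapies when the REP ends or later, "in order to ensure collection of AEs and concomitant therapies throughout the REP". The same section says of subjects who leave after dosing that "the data will be included in the CRF and will be reported in the CTR".

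**Protocol 5.2.6.2.1 (AE collection).** All AEs and AESIs must be documented in the CRF from informed consent until the individual subject's EoTrial. After EoTrial the site "does not need to actively monitor the subject for new AEs but should only report any occurrence of cancer and related SAEs and related AESIs" that come to its notice. It then adds: "Those AEs should, however, not be reported in the CRF". The section does not refer to 3.3.4.

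**Analysis text.** Protocol 1.2.6 sets the REP at 16 weeks. Protocol 7.3.4 and SAP 6.1 assign AEs from dosing to the end of the REP to treatment. Protocol 7.3.4 sends only AEs that occur after the last per protocol contact to Pharmacovigilance alone, outside the trial database.

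**The concern.** The two sections give different answers for the same subject. Section 3.3.4 sets up a contact whose purpose is complete AE collection over the REP. Section 5.2.6.2.1 closes mandatory CRF collection at an EoTrial examination that, for this subject, has already taken place, and it directs some of what the contact may find away from the CRF. It is the section a site would consult for AE collection.

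The secondary endpoints are the occurrence of treatment-emergent AEs and of drug-related AEs. SAP 7.8.1 counts subjects with AEs, SAP 7.8 reports leavers' safety data as far as available, and SAP 7 bases percentages on everyone in the analysis set. A leaver whose later event never reaches the database stays in the denominator and appears event-free after the early EoTrial. The events 5.2.6.2.1 most clearly keeps out, related SAEs and related AESIs, are the ones that would feed the drug-related and serious-AE summaries.

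**Working it through.** The plan gives no figure to reproduce. The check compares the texts, then applies calendar arithmetic.

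**1. Does EoTrial come before the REP contact?** Yes. Section 3.3.4 puts the examination at discontinuation and the questioning at or after the end of the REP. The Flow Chart notes (S.C. note 12, I.V. note 13) define EoTrial as a set of examinations, and 6.2.3 calls it a visit. It is not a general term for the last contact. Section 6.2.2 also describes AE assessment as running from screening to the EoTrial examination.

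**2. What happens to an AE found at the contact?**

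| Event with onset after an early EoTrial, within the REP | 5.2.6.2.1 | 7.3.4 and SAP 6.1 |
|---|---|---|
| Cancer, related SAE, related AESI | Report to sponsor, not in the CRF | Treatment-emergent |
| Any other AE | Not on the post-EoTrial list; no stated CRF route, not expressly barred | Treatment-emergent |

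**3. Which subjects?** REP = 16 × 7 = 112 days, so it ends on Day 113. Scheduled EoTrial is Day 176, which is 63 days later, so completers are unaffected. Uncovered days = 113 − EoTrial day:

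- Day 29: 84 days (84/112 = 75.0%)
- Day 57: 56 days (50.0%)
- Day 92: 21 days (18.8%)
- Day 120 or later: none

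**4. Weight of one missed subject.** 1/10 = 10.0 percentage points in a dose group of 10, or 1/11 = 9.1 if a replacement brings the treated number to 11. In the planned totals it is 1/20 = 5.0 (Total sc) and 1/30 = 3.3 (Total iv).

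**5. Chance that a leaver's first AE falls in the gap.** Assume a constant AE rate, with p the proportion of subjects having an AE by Day 113. Then L = −ln(1 − p)/112, and the chance is exp(−L·t) − exp(−L·112), with t = EoTrial day − 1. The lower value, p = 3/18 = 16.7%, is the rate on IV spesolimab in trial 1368-0009 (protocol 1.2.5; the follow-up length is not given). The upper value, p = 50%, is an assumption.

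| EoTrial day | p = 16.7% | p = 50% |
|---|---|---|
| 29 | 0.955 − 0.833 = 0.122 | 0.841 − 0.500 = 0.341 |
| 57 | 0.913 − 0.833 = 0.080 | 0.707 − 0.500 = 0.207 |
| 92 | 0.862 − 0.833 = 0.029 | 0.569 − 0.500 = 0.069 |

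One reachable leaver at Day 29 gives 0.12 to 0.34 expected missed subjects. Three give 0.37 to 1.02. These are upper figures, because they assume that the site records no AE from the contact.

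**The case against.** The best defence is that the texts cover different channels. The post-EoTrial rule in 5.2.6.2.1 concerns events the investigator happens to hear of, whereas 3.3.4 prescribes one planned questioning for a narrow group and states its purpose. A specific provision would normally govern a general one. Section 3.3.4 also says that the data of subjects leaving after dosing go into the CRF, and it sets longer collection for subjects removed because of pregnancy. In 7.3.4, the last per protocol contact is best read as including the 3.3.4 questioning. Most of the plan therefore points towards collection.

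Much of this stands, and it rules out two stronger readings. A reader might infer that 5.2.6.2.1 bars every AE from the CRF after EoTrial. It does not: the exclusion refers back to cancer, related SAEs and related AESIs, and the rule up to EoTrial is a required minimum. A reader might also take the screening-failure exception in 5.2.6.2.1 as proof that leavers were deliberately left out. That clause only removes undosed subjects' data from the CRF and does not address collection after EoTrial.

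What the defence does not remove is the express CRF exclusion for the listed events. Nothing in the documents lifts it for a subject whose EoTrial falls inside the REP. Section 5.2.6.2.3 requires AEs to be followed up, including those persisting after EoTrial, but does not reopen the CRF for new ones. CRF completion instructions might settle the matter, but they are not among the documents.

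**Conclusion.** The plan is wrong as written on this point, with a small effect. For dosed subjects who leave the trial before about Day 113, a stated rule keeps some treatment-emergent events out of the trial database, and for other AEs the CRF route is left open.

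Several things limit the size:

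- Subjects who only stop treatment are not the issue: "Even if the trial treatment is discontinued, the subject remains in the trial", given their agreement.
- AEs before the early EoTrial are kept, and related SAEs and AESIs still reach the sponsor.
- The contact is conditional, so some loss is accepted by design and would remain after the fix.
- Safety analysis is descriptive, with no hypothesis test.
- Few leavers are likely: all 48 subjects in trial 1368-0029 completed observation.

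One missed subject is 10 points in a group of 10, but even for a reachable leaver at Day 29 the chance of this is 12% to 34% under the assumptions above. A reader might treat the 10 permitted replacements as a forecast of leavers and infer a material bias. Section 7.7 gives that number only as a ceiling, and the documents state no expected number of leavers.

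**What to change.** In protocol 5.2.6.2.1, add wording to this effect: *For dosed subjects who leave the trial before the end of the REP, all AEs with onset up to the end of the REP, including those found at the contact described in section 3.3.4, are documented in the CRF. The post-EoTrial CRF exclusion applies only after the later of EoTrial and that contact.* In 7.3.4, confirm that this contact counts as a per protocol contact.

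The cost is two sentences in 5.2.6.2.1, one in 7.3.4, and a CRF entry for a contact the protocol already requests. No visit, sample or analysis is added.
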